5.3. Randomization and Blinding

This is a randomized, double-blind, placebo-controlled study; therefore, access to treatment allocation will be limited to unblinded members of the study team only. Treatment arm assignment will be blinded to patients, site study team, Sponsor study team, Contract Research Organization (CRO) study teams, and Investigators. Study drugs will be dispensed in a blinded fashion to the patients.

For the Phase 2 part of the study, a total of approximately 80 patients will be randomized in a 1:1 ratio (active epetraborole tablets: matching placebo tablets) using an IRT system and stratified by baseline use of ALIS and age at informed consent (<65 years versus ≥65 years). For the Phase 3 part of the study, a total of approximately 234 patients will be randomized in a 2:1 ratio (active epetraborole tablets: matching placebo tablets) using an IRT system and stratified by baseline use of ALIS and presence or absence of any fibrocavitary disease.

Blood samples will be collected from all patients in a blinded manner. Unblinded personnel will analyze the PK results.

After the last patients in Phase 2 and Phase 3 complete the Month 6+1 Week and Month 6 visits, respectively, prespecified members of the Sponsor and non-Sponsor analysis teams will be unblinded to treatment assignment for data analyses; study staff conducting psychometric validation analyses will remain blinded. Patients, Investigators, and other study staff will also remain blinded to treatment assignment through the last study visit (LFU) (see Study Blinding Plan).

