Results from the Phase 2 part of the study ongoing will inform the specific PRO and the clinical response definition selected to measure the primary endpoint, and the sample size re-estimations to be used, in the Phase 3 part of the study.

2.2.2 *Number of Patients*

A total of approximately 314 patients will be enrolled in this Phase 2/3 study:

- The Phase 2 part of the study will consist of approximately 80 patients randomized in a 1:1 ratio (40 patients in the epetraborole + OBR group and 40 patients in the placebo + OBR group). Randomization will be stratified by baseline use of ALIS and age at informed consent (<65 years versus \geq 65 years).
- The Phase 3 part of the study will consist of approximately 234 patients randomized in a 2:1 ratio (156 patients in the epetraborole + OBR group and 78 patients in the placebo + OBR group). Randomization will be stratified by baseline use of ALIS and the presence or absence of any fibrocavitary disease. The number of patients in the Phase 3 part of the study may be adjusted based on the results of Phase 2 analyses.

2.2.3 *Study Duration*

For the Phase 2 and Phase 3 parts of the study, the duration of study participation for each patient, not including Screening, will be up to approximately 19 months (see additional details in Protocol Section 3.1.1). Study participation for each patient includes the following:

- **Screening Visit:** Within 8 weeks prior to randomization.
- **Treatment Period:** Day 1 to EOT; the treatment period for each patient will vary, up to a maximum of 16 months, depending on the patient's sputum culture results; see details in Protocol Section 3.1.1.
- **EOT Visit:** Within 7 calendar days after the last dose of study drug.
- **LFU Visit:** 3 months (84 days \pm 14 days) after the last dose of study drug.

2.2.4 *Sites*

This Phase 2/3 study will be conducted globally at approximately 140 sites.

2.2.5 *Study Drug*

- Epetraborole oral tablets: 250 mg
- Epetraborole dosage: 500 mg (two 250-mg oral tablets) once daily (QD)
- Placebo oral tablets: Matched to epetraborole tablets

- Placebo regimen: Matched to epetraborole dosage [two oral tablets once daily (QD)]

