Phase 3: No data are available on symptom-based clinical response or minimal clinically important differences (MCIDs) using available PROs in patients with treatment-refractory MAC lung disease; therefore, previously published Month 6 sputum culture conversion rates in treatment-refractory MAC lung disease were used to initially estimate the number of patients expected to have an MCID improvement in PRO score, assuming a correlation between microbiological response and clinical symptom improvement. A Phase 3 study comparing ALIS + OBR versus OBR alone in patients with treatment-refractory MAC lung disease reported Month 6 sputum culture conversion rates of 29.0% compared with 8.9%, respectively, in the ITT population. Therefore, the initial sample size estimate for the Phase 3 part of the study assumes that the true number of patients experiencing an MCID improvement in PRO score is 30% for the epetraborole + OBR arm and 10% for the placebo + OBR arm. Assuming a 2:1 randomization and a 2-sided alpha of 0.05, a Phase 3 study of 186 patients with proven MAC lung disease (ie, in the Micro-ITT population) in the primary analysis (124 patients in the epetraborole + OBR arm and 62 patients in the placebo + OBR arm) would provide approximately 90% power, while also assuming when performing an analysis of proportions using the method of Miettinen and Nurminen. The total sample size for the Phase 3 part of the study is estimated to be 234 patients (156 patients in the epetraborole + OBR arm and 78 patients in the placebo + OBR arm) rather than 186 patients, to allow for approximately 20% of randomized patients to be excluded from the Micro-ITT Population due to lack of a study qualifying baseline culture (see Inclusion Criterion 3.a in Protocol Section 4.1); therefore, 186 patients are expected to be included in the Micro-ITT Population for the primary efficacy analysis. The sample size for Phase 3 will be reassessed after Phase 2 analyses, which will be based on data for all patients in Phase 2 through Month 6. Any needed sample size adjustment for Phase 3 will be determined by the Sponsor as part of the review of unblinded results from the fully independent Phase 2 data.

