For each of the three Phase 3 endpoints above, a hierarchical testing approach will be applied, whereby the primary endpoint will be tested, and if superiority is concluded for the primary endpoint, the second and third named endpoints above will then be tested, in order. As no specific claims are intended for other secondary endpoints, no further multiplicity testing will be applied for the other secondary and exploratory endpoints. Furthermore, as any modifications to the Phase 3 primary efficacy or key secondary endpoints in each region are based strictly on data obtained from the fully independent Phase 2 patient analysis population, no adjustment to the overall alpha level of 0.05 for testing the primary efficacy or hierarchically tested secondary endpoints is necessary.

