QOL-B respiratory domain scores are measured on a scale from 0 to 100 (with higher scores indicating better health-related quality of life). QOL-B respiratory domain scores will be summarized by visit in the Micro-ITT Population. Descriptive statistics of both the reported QOL-B respiratory domain scores and change from baseline will be reported by visit (monthly through Month 6). Change from baseline to Month 6 in QOL-B respiratory domain score will be analyzed using an analysis of covariance (ANCOVA) model, including baseline score, treatment and either including (primary analysis) or excluding (sensitivity analysis 1) stratification factors of baseline ALIS use and the presence or absence of any fibrocavitary disease as covariates. Least squares means, 95% confidence intervals, and p-values of the treatment comparison will be presented for both the Micro-ITT (primary) and PP (sensitivity) populations.

Patients who fail to provide a complete QOL-B respiratory domain score at both baseline and Month 6 will be excluded from the analysis and considered unbiased under the missing at random (MAR) assumption, with the exception of patients experiencing intercurrent events, which will be accounted for following the imputation rules above. However, in an additional pair of sensitivity analyses, the primary efficacy analysis will be repeated as described above, but applying a treatment policy strategy in which results for patients with new, additional non-study-specific, antimycobacterial therapy that is potentially effective against MAC, or surgery for MAC lung disease, for reasons other than clinical failure of study drug, will be used as recorded. These models will be run using the ANCOVA model as described above, including baseline score, treatment and either including (sensitivity analysis 2) or excluding (sensitivity analysis 3) stratification factors of baseline ALIS use and the presence or absence of any fibrocavitary disease as covariates.

3.4.3.2 Phase 3 Primary Efficacy Endpoint Outside the US (Key Secondary Endpoint in the US)

The primary efficacy outside the US (secondary in the US) is by-patient sputum culture conversion monthly through Month 6. The Estimand corresponding to the primary endpoint is defined with the following five attributes:

1. Population: Patients with MAC culture-positive Pre-Study and Screening respiratory specimens

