Descriptive statistics of both the reported scores and change from baseline (for continuous scores only) will be reported by visit (monthly through Month 6) for scores for all PROs collected in the study (QOL-B domain scores, MACrO₂ total scaled score, NTM Symptoms Module, SGRQ-C, PGIS, PGIC, CGIS, CGIC, and Meaningful Change Question) based on the Micro-ITT Populations. Change from baseline score at Month 3 and Month 6 of selected continuous PROs including QOL-B respiratory domain score (Month 3 only, as Month 6 is the primary efficacy analysis), MACrO₂ total scaled score, NTM Symptoms Module domain score, and SGRQ-C total score will be analyzed using an analysis of covariance (ANCOVA) model, including baseline score, treatment and stratification factors (baseline ALIS use and presence or absence of any fibrocavitary disease) as covariates. Least squares means, 95% confidence intervals, and p-values of the treatment comparison will be presented for both Micro-ITT and PP populations. Intercurrent events will be handled following the same rules as for the primary efficacy analysis.

Clinical response as defined above for the MACrO₂ PRO as well as for each additional PRO measure according to pre-defined response thresholds relative to baseline will be examined monthly through Month 6. MACrO₂ original responder is defined as improvement of ≥ 1 grade in the key symptom with no worsening of other symptoms. Response in QOL-B respiratory domain score is defined as an improvement

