3.4.3.4 Phase 3 Exploratory Efficacy Endpoints

In an exploratory analysis, descriptive statistics for least-square mean difference of change from baseline in QOL-B respiratory domain score and MACrO₂ total scaled score, and by-patient sputum culture conversion by Month 6 will be presented by age category, ALIS use at baseline, presence-absence of any fibrocavitary disease, chest cavity category (non-cavitary, cavity diameter ≤ 3 cm, cavity diameter > 3 cm from EDC), MAC resistance phenotype (ie, macrolide-resistant, amikacin IV-resistant, and amikacin (liposomal, inhaled)-resistant), sex, baseline creatinine clearance category (<60 mL/min, ≥60 mL/min to <90 mL/min, or ≥ 90 mL/min), BMI category (<18.5 vs ≥18.5 kg/m²), and country of enrollment in the Micro-ITT Population. Forest plots of the estimated treatment difference and 95% confidence interval will be presented across all subsets, but no formal statistical testing will be performed.

Change from baseline in continuous PROs, including QOL-B respiratory domain score, MACrO₂ total scaled score, NTM Symptoms Module Domain score, and SGRQ-C total score, will be analyzed using a mixed model for repeated measures (MMRM) that includes randomized treatment, visit (from Baseline to Month 6 inclusive), and treatment by visit interaction as explanatory variables, and corresponding baseline score as a continuous covariate. Treatment visit and treatment by visit interaction will be fixed effects in the model, and treatment by visit interaction will remain in the model regardless of significance. The participant effect will be fitted as a random effect and an unstructured covariance structure will be assumed for within participant variation. If this model does not converge then the covariance matrices of Toeplitz, first-order autoregressive, and compound symmetry will be used in that order until the model converges. The analysis will be performed using PROC MIXED in SAS and the resulting F-tests will be based on Kenward-Roger's adjusted degrees of freedom. Least squares means, 95% confidence intervals, and p-values of the treatment comparisons at Month 3 and Month 6 will be presented for both Micro-ITT and PP populations, along with an assessment of the difference between slopes from baseline to Month 6 and residual plots will be provided to examine departures from normality and/or outliers.

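### Under 2:1 allocation the standard error of the Phase 3 ANCOVA is not robust to unequal residual variances between arms, and no planned sensitivity analysis relaxes that assumption

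*SAP*

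**What the plan says.** Protocol 5.3 states that for Phase 3 "a total of approximately 234 patients will be randomized in a 2:1 ratio", active to placebo. Phase 2 was randomised 1:1.

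SAP 3.4.3.1 makes change from baseline to Month 6 in QOL-B respiratory domain score the US primary endpoint. The model is an ANCOVA with baseline score, treatment and the two stratification factors (baseline ALIS use and fibrocavitary disease). On its output the section says: "Least squares means, 95% confidence intervals, and p-values of the treatment comparison will be presented for both the Micro-ITT (primary) and PP (sensitivity) populations". It does not say how the standard error is estimated. Sensitivity analysis 1 drops the stratification factors. Analyses 2 and 3 change the handling of intercurrent events, with and without those factors. Patients lacking a baseline or Month 6 score are left out.

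SAP 3.4.3.3 uses the same model for other continuous PROs, including the MACrO2 total scaled score: change "will be analyzed using an analysis of covariance (ANCOVA) model, including baseline score, treatment and stratification factors". SAP 3.4 ranks that score second in the US hierarchy and holds that "no adjustment to the overall alpha level of 0.05 for testing the primary efficacy or hierarchically tested secondary endpoints is necessary".

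The only model diagnostic is attached to the exploratory MMRM in SAP 3.4.3.4, where "residual plots will be provided to examine departures from normality and/or outliers". That model has an unstructured covariance over visits and no separate covariance by arm.

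**The concern.** An ANCOVA with no further provision estimates one residual variance for both arms. With equal arms this does little harm: even if the true variances differ, the pooled estimate gives nearly the right standard error for the difference. With 2:1 allocation that protection is lost. The pooled variance is weighted towards the larger epetraborole arm, whereas the true variance of the difference is weighted towards the smaller placebo arm.

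If placebo residuals are the more spread, the interval is too narrow and the 0.05 level is exceeded. If epetraborole residuals are the more spread, the interval is too wide and the test loses power.

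The QOL-B test opens the US hierarchy, so its result decides whether the MACrO2 score and culture conversion are tested at all. Outside the US, QOL-B and the MACrO2 score rank second and third. Unequal spread is possible, since the score is bounded at 0 and 100 and treatment may help some patients and not others.

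**Working it through.** **The plan's own figure.** SAP 2.2.7 gives about 90% power for 124 versus 62 patients at 30% versus 10%: "Assuming a 2:1 randomization and a 2-sided alpha of 0.05". The usual two-proportion formula gives 89.7%, and exact enumeration of the unstratified Miettinen-Nurminen test gives 90.7%, so the figure reproduces. It belongs to the superseded binary endpoint and does not bear on the ANCOVA. The documents state no power and no SD for QOL-B.

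**Inputs.** Planned Micro-ITT sizes are 124 and 62 (SAP 2.2.7), and alpha is 0.05 two-sided. The ratio r of epetraborole to placebo residual SD is an assumption, varied from 0.67 to 1.5.

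**Formula.** With placebo SD set to 1:

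- True variance of the difference: r²/124 + 1/62.
- Expected model-based variance: [(123r² + 61)/184] × (1/124 + 1/62).
- k = square root of (model-based / true).
- Type I error = 2 × [1 − Φ(1.96k)].

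At r = 0.8:

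- True variance: 0.64/124 + 1/62 = 0.02129.
- Model-based variance: (139.72/184) × 0.02419 = 0.01837.
- k = √(0.01837/0.02129) = 0.929, so the standard error is about 7% too small.
- Type I error = 2 × [1 − Φ(1.82)] = 6.9%.

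**Simulation.** The ANCOVA was simulated under no treatment effect, with baseline, two binary factors, normal errors and 20,000 runs per case. The model-based and HC3 standard errors were both referred to a t distribution on residual degrees of freedom.

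| SD ratio r | k | Type I, formula | Model-based, simulated 124/62 | HC3, simulated 124/62 |
|---|---|---|---|---|
| 0.67 | 0.878 | 8.5% | 8.9% | 5.2% |
| 0.83 | 0.941 | 6.5% | 6.2% | 4.6% |
| 1.0 | 1.000 | 5.0% | 4.8% | 4.6% |
| 1.2 | 1.062 | 3.7% | 3.8% | 4.7% |
| 1.5 | 1.138 | 2.6% | 2.6% | 4.3% |

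Further model-based runs at 124/62 gave 6.6-6.9% at r = 0.8 (formula 6.9%) and 6.1% at r = 0.9 (formula 5.8%).

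**Does sample size matter?** At 62/31, the simulated model-based type I errors for the same five ratios are 8.3%, 6.3%, 5.0%, 3.9% and 2.8%, and HC3 gives 4.3-4.7%. The distortion comes mainly from the allocation ratio.

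**Does the ratio matter?** At 93/93 the formula gives 5.0% for every r, and the simulated model-based values are 5.1-5.3%.

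**The case against.** The strongest reply is that nothing in the documents shows the arms' spread to differ. No QOL-B SD is given for either arm. A 10% difference moves type I error by only about one point, and inflation needs placebo to be the more variable arm. A ceiling at 100 could produce that, but patients enter with at least two symptoms and a key symptom of moderate or greater severity (Protocol 4.1), so a strong ceiling effect is speculative. A mix of responders and non-responders on active treatment would work the other way. The one arm-level result reported, MACrO2 response of 39.5% versus 25% in Phase 2 (SAP 1), gives binary SDs of √(0.395 × 0.605) = 0.489 and √(0.25 × 0.75) = 0.433, a ratio of about 1.13. This is a different instrument and only weak evidence, but it points to the conservative side. All of this stands, and it limits the size of the point.

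The SAP also has partial safeguards. SDs are among the standard summaries (SAP 3.1.3), mean and SD of change are plotted by arm, and QOL-B response at 8 and 11.1 points is compared by Miettinen-Nurminen (SAP 3.4.3.3). These could reveal unequal spread or give a result free of the ANCOVA variance. They do not correct the p-value of the test that opens the hierarchy.

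A common residual variance is inferred from the word ANCOVA. The SAP does not state it, and the programming specifications are a separate document (SAP 6). The inference is the ordinary reading, and an unstated choice would itself need stating.

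**Conclusion.** There is a modest, conditional robustness gap in the US primary analysis and in the second-ranked MACrO2 analysis. Under 2:1 allocation the model-based standard error depends on equal residual variances, and the planned sensitivity analyses and the Per-Protocol repeat share that dependence. The sizes above rest on assumed SD ratios and on 2:1 holding among the patients analysed. Leaving out patients without complete scores may shift that ratio. Early termination (SAP 1) reduces numbers but does not by itself remove the dependence.

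A reader might infer more than this:

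- **That the planned interval and p-value are wrong, or that the 0.05 level is exceeded.** The documents support neither. The error is nil at equal SDs, small at a 10% difference, and conservative if epetraborole is the more variable arm.
- **That a definite amount of power is lost.** That would need a treatment effect and SDs for QOL-B, which the documents do not give, and the final Phase 3 numbers per arm, which they do not report.
- **That the model was taken over from the 1:1 Phase 2 without thought.** SAP 3.4.1.3 does use the same form, but the documents say nothing about why it was chosen for Phase 3.

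**What to change.** Before Phase 3 unblinding, add one sentence to SAP 3.4.3.1 and 3.4.3.3: the standard error, confidence interval and p-value of the ANCOVA treatment contrast use the HC3 heteroscedasticity-consistent estimator, with the model-based standard error reported alongside as a sensitivity analysis. If the sponsor prefers to keep the model-based result as primary, prespecify the HC3 version as a sensitivity analysis for both endpoints.

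Timing matters. SAP 1 sends deviations after Phase 3 unblinding to a post hoc addendum or the study report, and an estimator chosen after the arm SDs are known would be data-driven.

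The cost is one sentence per section and one program option. If the SDs are equal, HC3 gives up roughly half a point of power, simulated at 124/62 with an assumed effect of 0.5 SD, a figure that is not in the documents.

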3.1.1. Duration of Study Drug Administration and Study Participation

For the Phase 2 and Phase 3 parts of the study, the duration of study participation for each patient, not including Screening, will be up to approximately 19 months as described in [Section 3.1](#).

Each patient's duration of study participation will vary depending on the timing of microbiological sputum MAC culture conversion. To receive study drug beyond Month 6, a patient must have achieved a microbiological sputum MAC culture conversion.

All patients will receive a minimum of 6 months of blinded study drug treatment. At the Month 6 Visit, all available sputum culture results will be assessed by the Investigator to determine whether a patient is a converter or non-converter. A converter is defined as a patient who has 3 consecutive monthly MAC-negative sputum cultures at any time within the first 6 months of the study. A non-converter is a patient who does not have 3 consecutive monthly MAC-negative sputum cultures at any time within the first 6 months of the study.

Patients who are assessed as converters will continue taking blinded study drug for 12 months after the first month that defines sputum culture conversion, up to a maximum of 16 months. Patients who are assessed as non-converters will discontinue study drug at the Month 6 Visit. Patients who are discontinued from study drug at the Month 6 Visit will complete the EOT Visit at this time point, as well as the MACrO₂ and PGIS 1 week (+1 day) after their EOT Visit, and an LFU Visit 3 months (84 days \pm 14 days) after the last dose of study drug.

Because reporting of final respiratory culture and identification results may occur up to 8 weeks after specimen receipt at the regional or central microbiological laboratory, it is unlikely that the Month 5 culture results will be available at the Month 6 Visit. Patients who have negative culture results from Month 4 and no culture data available from Month 5 will be presumed to be converters and will continue blinded study drug at the Month 6 Visit. Such patients subsequently found to have positive cultures from the Month 5 and/or Month 6 visit must be discussed with the Medical Monitor for determination of continued study drug therapy beyond Month 6. Patients with *missing* sputum cultures from any visit prior to Month 6 should not be prematurely

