5.8.3. Prohibited Prior and Concomitant Therapy

The following medications and treatments are prohibited:

- Any anticipated or planned lung surgery for MAC lung disease
- Immunosuppressive therapy use at Screening and throughout the Treatment Period that in the opinion of the Investigator may place the patient at risk for an opportunistic pulmonary infection, including transplant rejection medication and chronic systemic corticosteroids defined as ≥ 20 mg/day of prednisone or systemic equivalent for >4 weeks. Short-term use of corticosteroids (eg, glucocorticoid taper for treatment of COPD exacerbation) is allowed.
- Chemotherapy or radiation therapy within 1 year prior to randomization through the LFU Visit

- The addition of a new non-study-specific, antimycobacterial therapy (eg, macrolides, rifamycins, ethambutol, aminoglycosides, fluoroquinolones, oxazolidinones, trimethoprim-sulfamethoxazole, clofazimine, isoniazid) to treat the index MAC infection is not allowed for reasons other than microbiological failure.

If the Investigator believes that a potentially MAC-active agent is required to treat a non-MAC infection, the case should be discussed with the Medical Monitor prior to administration. Premature discontinuation of study drug or withdrawal from study should be avoided in these cases. See [Section 5.7](#) for OBR details.

- Participation in a clinical trial of an investigational agent within 30 days (or 5 half-lives, whichever is longer) prior to Screening and throughout the Treatment Period

The use of concomitant drugs with the potential to cause anemia should be avoided when feasible. Any questions regarding the use of concomitant non-study-specific therapy should be directed to the Medical Monitor prior to administration.

Any patient who receives prohibited therapy will be excluded from the Per-Protocol Population; see the SAP(s) for more details.

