All efficacy endpoints described below will be assessed at exactly one analysis stage (either the Month 6 Analysis or the End of Study Analysis in Phase 2, or in the single End of Study Analysis in Phase 3) and not repeated subsequently, in order to control the type one error level of the overall study conclusions in each phase. As the primary and key secondary endpoints for both US and outside the US regulatory agencies are based on endpoints collected through Month 6 for both Phase 2 and Phase 3, the formal study objectives are expected to be assessed and reported to regulatory authorities at the time of the Month 6 Analysis from Phase 2. All efficacy endpoints assessed at the End of Study Analysis in Phase 2 are identified as additional secondary or exploratory endpoints and are thus considered supportive in nature. Per the revised approach to Phase 3, a single End of Study analysis for all patients in Phase 3 will be performed after the overall study database has been locked, with all endpoints through the LFU visit assessed at this single analysis phase.

The analyses and presentations of Phase 2 data to support the assessment of the measurement properties of the novel MACrO₂ PRO and published QOL-B RD score and to provide validation evidence in treatment-refractory NTM lung disease are not included within the SAP, but are outlined in separate Psychometric Analysis Plans (PAPs) for each of the MACrO₂ and QOL-B RD PROs. All analyses outlined in this SAP refer to the analyses to estimate the effect of treatment from the Phase 2 data and the Phase 3 data.

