2. Treatment: Epetraborole oral tablets 500 mg (two 250 mg oral tablets) QD + OBR or placebo oral tablets QD matched to epetraborole dosage + OBR
3. Variable: Sputum conversion rate is defined as proportion of patients having culture conversion based on 3 consecutive monthly negative sputum cultures for MAC by Month 6
4. Intercurrent events:
 - a. New, additional non-study-specific, antimycobacterial therapy that is potentially effective against MAC for reasons other than clinical failure of study drug: data collected after such therapy will not be used and patients will be classified as a failure for microbiological response (composite strategy)
 - b. Surgery for MAC lung disease for reasons other than clinical failure of study drug: data collected after such surgery will not be used and patients will be classified as a failure for microbiological response (composite strategy)
 - c. Permitted medications/interventions and or prohibited medications/interventions other than those described in bullets a and b: microbiological response data collected after permitted or other prohibited medications/interventions administration will be used as recorded (treatment policy strategy)
 - d. Inadequate compliance: patient data will be used as recorded (treatment policy strategy)

5. Population-level summary: Difference between epetraborole + OBR and placebo + OBR in sputum conversion rate by Month 6.

“Microbiological response” is defined as sputum culture conversion based on 3 consecutive monthly negative sputum cultures for MAC by Month 6. By-patient microbiological response will be presented for the Micro-ITT Population by Month 6. Descriptive statistics (n, %) will be presented by treatment group, along with the treatment difference (i.e. epetraborole + OBR response percentage minus placebo + OBR response percentage), associated 95% confidence interval and p-value, calculated using the method of Miettinen and Nurminen, both including (primary analysis) and excluding (sensitivity analysis) stratification by baseline ALIS use and the presence or absence of any fibrocavitary disease.

3.4.3.3 *Secondary Efficacy Endpoints*

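### The Phase 3 culture-conversion estimand puts no timing condition on MAC-active therapy or surgery, so an event after the third negative culture but before Month 6 cancels a conversion already shown

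*SAP*

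**What the plan says.** SAP 3.4.3.2 defines the variable as the "proportion of patients having culture conversion based on 3 consecutive monthly negative sputum cultures for MAC by Month 6". Protocol 3.1.1 likewise calls a patient a converter on "3 consecutive monthly MAC-negative sputum cultures at any time within the first 6 months of the study". The third negative can therefore fall at Month 3, 4, 5 or 6.

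Item 4a of the estimand is triggered by "New, additional non-study-specific, antimycobacterial therapy that is potentially effective against MAC for reasons other than clinical failure of study drug". Its consequence has two parts: data after such "therapy will not be used and patients will be classified as a failure for microbiological" response. Item 4b applies the same two parts to surgery for MAC lung disease. Both are labelled composite strategies. Neither item gives a start window or an exception for a patient who had already converted.

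The trigger is foreseeable. Protocol 5.8.3 anticipates a potentially MAC-active agent for a non-MAC infection, after discussion with the Medical Monitor, and adds: "Premature discontinuation of study drug or withdrawal from study should be avoided in these cases". SAP 3.3.6 plans a summary of antibiotics of this kind, in terms close to the item 4a trigger, and has antibiotics recorded throughout study participation.

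SAP 3.4 replaces the two-stage Phase 3 analysis with one End of Study analysis, "with all endpoints through the LFU visit assessed at this single analysis phase".

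**The concern.** Discarding later cultures would, on its own, leave an earlier conversion standing. The second part, classification as a failure, overrides it. For an event that starts after the third negative culture, the rule reverses a result that the event could not have influenced.

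Only converters can be affected, because everyone else is a failure already. The endpoint concerned is the primary outside the US and the third step of the US hierarchy.

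The SAP handles the same event differently for the QOL-B respiratory domain score (3.4.3.1). There, only scores after the event are replaced, by the last score before it. QOL-B also has treatment-policy sensitivity analyses (numbers 2 and 3). Conversion has only a comparison with and without stratification, so nothing planned would show the effect of the rule.

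**Working it through.** **1. The plan's own figure.** Inputs from SAP 2.2.7: 124 and 62 Micro-ITT patients, rates of 30% and 10%, two-sided alpha 0.05, Miettinen-Nurminen method, about 90% power. Exact enumeration of the unstratified Miettinen-Nurminen test gives 0.907, and the normal approximation gives 0.897. The stated power is reproduced. The rates were set for PRO response and borrowed from published conversion rates. Expected converters: 124 × 0.30 = 37.2 and 62 × 0.10 = 6.2.

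**2. Time at risk between conversion and Month 6.** Visits are 28 days apart. Conversion on Months 1–3, 2–4, 3–5 or 4–6 leaves 84, 56, 28 or 0 days. If the four windows are equally likely (an assumption), the mean is (84 + 56 + 28 + 0)/4 = 42 days = 0.115 year.

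**3. Share of converters reclassified.** The event rate λ is assumed, constant over time and equal in the two arms. Share f = 1 − exp(−λ × 0.115); remaining difference = 20 × (1 − f) points.

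| λ per patient-year | f | Rates (%) | Difference (points) |
|---|---|---|---|
| 0.2 | 2.3% | 29.3 v 9.8 | 19.5 |
| 1.0 | 10.9% | 26.7 v 8.9 | 17.8 |

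At λ = 1.0 this is 37.2 × 0.109 = 4.0 epetraborole converters and 6.2 × 0.109 = 0.7 placebo converters.

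**4. Power.** With 2% of converters cancelled in both arms, Miettinen-Nurminen power is 0.900; with 10% it is 0.865; with none, 0.907. A second calculation used start rates of 0.5% to 3% per 28-day month (about 0.07 to 0.39 per year) and averaged over the four windows. It gives 0.7% to 4.3% cancelled by Month 6 and power of 0.905 to 0.891.

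**5. Unequal event rates.** As an extreme illustration, if only the epetraborole arm lost 10.9% of its converters, the difference would be 26.7 − 10 = 16.7 points. If only placebo did, it would be 30 − 8.9 = 21.1 points.

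**6. The rule applied to one patient.** Negative at Months 1, 2 and 3: converted by Day 85 under Protocol 3.1.1. MAC-active antibiotic for a non-MAC infection at Month 5: item 4a applies and the patient is a failure. Under the QOL-B rule, the same event would leave every score before Month 5 unchanged.

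**The case against.** **It is a declared composite strategy.** Success can be defined as conversion without other MAC-active therapy. That is a different target rather than an estimation error. With equal event rates the null hypothesis is preserved, the ratio of the two rates is unchanged, and the test is conservative. This stands as far as it goes. It justifies failure for an event before conversion, where the event could have produced the negatives. It gives no reason for reversing a conversion completed earlier, and the SAP offers none.

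**The effect up to Month 6 is small.** This stands: 0.5 to 2.2 points on the assumed rates. The upper rate, one new MAC-active course per patient per year, is high for a protocol that restricts new antimycobacterials and routes such cases through the Medical Monitor. Phase 2 did not show superiority on conversion (SAP 1), so the true difference may be below 20 points, leaving fewer points to lose.

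**A stronger reading: the rule runs to Late Follow-up.** Because items 4a and 4b have no end date and Phase 3 has one lock, a reader might infer that therapy at Month 9, or after treatment ended, turns a Month 6 converter into a failure. Over a full planned year after conversion the loss would be much larger. The documents do not support building on this. The variable, the population-level summary and the response definition all say by Month 6, and an event after that cannot interfere with the variable. The single lock sets when analyses are run; it does not redefine the endpoint. The same items appear in the Phase 2 estimand, which suggests that they were carried over. A full year at risk also sits badly with a trial that began Phase 3 enrolment in September 2023 and was terminated on 08 August 2024. What remains is that the Month 6 limit has to be inferred.

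**A second stronger reading: bias is always toward no difference.** That requires similar event rates by arm, which the documents do not establish.

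**Conclusion.** The point holds on the text. As written, items 4a and 4b cancel conversions shown entirely by cultures that pre-date the event, and they leave the Month 6 limit unstated. On assumed rates of 0.2 to 1.0 courses per patient-year, evenly spread conversion times, equal rates by arm and the 30% v 10% planning rates, about 2% to 11% of converters would be reclassified by Month 6 and the difference would be 19.5 to 17.8 points instead of 20. The loss would be larger only if events after Month 6 were counted, which is the less likely reading. The planned 186 patients are used because the documents do not give the Phase 3 number analysed after termination.

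This should be fixed before Phase 3 unblinding, but it does not invalidate the endpoint. Two programmers could read the items differently. Under SAP 1, a departure from the current SAP after unblinding would have to be reported as such in an addendum or the study report.

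**What to change.** Replace the consequence in SAP 3.4.3.2 items 4a and 4b with:

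> Cultures collected after the start of such therapy or surgery are not used; the patient is a failure only if 3 consecutive monthly negative cultures were not completed before that start date; events starting after the Month 6 visit are ignored for this endpoint.

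This keeps the composite strategy for events before conversion and brings the rule into line with QOL-B, where only data after the event are replaced. Optionally, add one treatment-policy sensitivity analysis for conversion, matching QOL-B sensitivity analyses 2 and 3. The change is confined to Phase 3, as SAP version 3.0 requires.

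The cost is a short SAP edit and a date comparison in programming, with no new data. The downside is that a few patients who convert and then receive other MAC-active therapy before Month 6 will count as successes.
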